4.3.2 Non-Responder Imputation (NRI)

For categorical efficacy endpoints, non-responder imputation (NRI) will be used when the response status cannot be determined. Patients whose survival status cannot be determined at day 28 will be non-responders in the analyses of Complete Response.

4.3.3 Missing Data Imputation for Adverse Event, Concomitant Medication Dates, and Laboratory Values

If a medication date or AE date is completely or partially missing, the following imputation rules should be utilized in the analysis unless otherwise stated:

- For the start date:
 - If year, month, and day are missing then use the patient's first treatment date.
 - If either month or month and day are missing, then use the same month and day as treatment start.
 - If only day is missing, impute as day of treatment start.
- For the start time:
 - Impute as 23:59.

- For the end date:
 - If year, month, and day are missing then use the patient's last visit date. ○ If either month or month and day are missing then use December 31.
 - ○ If only day is missing then use the last day of the month.
 - The imputed date will not be beyond the patient's last visit date.

The incomplete dates will be imputed only if it is deemed necessary in calculation/determination for analysis purpose. If there is any doubt for the start and end date/times for AEs, the event will be flagged as treatment-emergent. For medications, the medication will be flagged as concomitant.

For determining treatment-emergent status, missing severity in the baseline period will be considered “mild” and missing severity in the post-baseline period will be considered “severe”. When reporting TEAEs by severity or causality, “missing” severity or causality will be considered its own category.

Laboratory parameters will be summarized based on the available data at each time point and no imputation is proposed in this document.

4.4 Handling of Deaths in Efficacy Analyses

For the endpoint that does not contain mortality as a component, such as length of hospital stay during Days 1 to 28, they will be assumed in the hospital for 29 days. The median length in such case will be more appropriated to be reported.

Other efficacy endpoints will handle death via similar imputation: patients who die will be assumed to have experienced the worst outcome. These analyses include percentage of patients discharged from hospital at Day 28, percentage of patients who ever received each of the various types of supportive care, and length of the various types of supportive care.

4.5 Multicenter Studies

While study center will be included as a covariate for some analyses, differences between study centers will not be a feature of the statistical analyses for this study. Baseline variables and demographics will be described by site.

ALL sites that have one or no patient in either treatment group will be pooled together as a single site. If there is only one site with one or no patient in either treatment group, it will be pooled with the next smallest site. If more than one sites with the same number of patients as the next smallest site, the one with the patient who enrolled the study last will be chosen for pooling.

4.6 Multiple Comparisons/Multiplicity

There are no planned adjustments for multiple efficacy endpoints or analyses.

4.7 Patient Disposition

The disposition of all enrolled patients will be summarized. The disposition of all randomized patients will be presented by level of stratification factors in randomization, by treatment group and overall. In addition, the reason for study discontinuation will be tabulated using the list of reasons provided in the eCRF. The disposition of randomized patients will be analyzed for the Efficacy population and the Safety population.

4.8 Patient Characteristics

Patient's baseline age, sex, race, height, body weight, body mass index, other baseline efficacy measures including NIAID ordinal assessment, FiO₂, respiratory rate, disease history, and preexisting conditions will be summarized using descriptive statistics by treatment arm, overall, and by study site (unpooled). These summaries will be based on both the Efficacy population and the Safety population. Patients who are missing measurements of the baseline variable being analyzed will not be included in the summary for that variable.

Patient height and weight will be collected prior to randomization. Both variables will be reported in metric units (height in cm and weight in kg) and will be summarized as continuous variables along with Body Mass Index (in kg/m²).

No statistical testing will be performed for comparisons of baseline characteristics.

4.9 Medical History

Medical history will be coded according to MedDRA. The number of subjects reporting medical history events will be summarized by treatment and overall, by system organ class, and preferred term. The summary will present the SOC in alphabetical order; while PTs within the SOC will be presented in order of overall decreasing frequency of occurrence overall.

4.10 Treatment Compliance

As all study drug doses will be administered at study site, treatment compliance per se will not be reported.

4.11 Concomitant Therapy

Concomitant medications will be defined as medications taken on or after the date of the first dose of study treatment. This includes all medications initially taken prior to the date of first dose of study treatment but with a stop date that is either missing or after the date of first dose of study treatment. Those medications where the stop date is documented as prior to the date of first dose of study treatment will be classified as prior medications. The prior medications will not be included in any summary reports.

Concomitant medications will be summarized and will be presented by anatomical therapeutic chemical drug classes (ATC level 4) using the latest version of the WHO drug dictionary.

4.12 Efficacy Analyses

4.12.1 Primary Outcome and Methodology

The primary outcome variable will be defined as follows:

- For patients who survive through day 28, the value is the number of days free of mechanical ventilation.
- For patients who do not survive through day 28, the value is set to -1.

If a patient is discharged from the hospital before day 28, and if the patient is still alive at day 28, then days between hospital discharge and Day 28 will be considered ventilator free. A table listing the counts of patients with each number of ventilator free days, including patients with -1 values due to death, will be presented by treatment group. The statistical method for this endpoint will be based on the Wilcoxon rank-sum test using the van Elteren test adjusting for the randomization stratification factors (age group, sex, and site).

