10.3.3. Efficacy Analyses

10.3.3.1. Primary Analyses

The Wilcoxon rank-sum analysis of the primary endpoint, death at day 28 and days free of mechanical ventilation within 28 days among survivors (VFDsurv), will use a scoring scheme with patients from the Efficacy Analysis Set who do better getting a higher score. We will assign a VFDsurv score of -1 to patients who die before 28 days. For those patients who survive to day 28 the VFDsurv score will be equal to the number of VFDs calculated according to the above definition. If a patient is discharged from the hospital before day 28, and if the patient is still alive at day 28, they will be credited with ventilator free days from the time of discharge until day 28. The statistical method for this endpoint will be based on the van Elteren test adjusting for the randomization stratification factors (age group, sex, and site).

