3.2 Determination of Sample Size

Approximately 210 patients may be enrolled in a 1:1 ratio to LY3127804 or placebo (105 per treatment group) in order that 200 patients complete the study. A sample size of 100 in each group will have 81% power to detect a difference between the placebo group and the LY3127804 group using a Wilcoxon rank-sum test with a 0.05 one-sided significance level. This powering is based on the following assumptions: intermittent mandatory ventilation (IMV) rate of 25% and mortality rate of 12.5% in the placebo group, 50% improvement in IMV rate and mortality rate for the LY3127804 group relative to placebo, and a mean difference (LY3127804 minus placebo) of 3.0 ventilator-free days where patients who die are assigned a value of -1.

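### No overall comparison of ventilator-free days adjusted for baseline NIAID score is planned: the primary test is valid, but a chance severity imbalance would go uncorrected, and the power gain from adjusting is uncertain

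*SAP*

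**What the plan says.** - **Primary test.** SAP 4.12.1 scores deaths as -1 and compares the arms "using the van Elteren test adjusting for the randomization stratification factors (age group, sex, and site". Protocol 10.3.3.1 names the same method, a "van Elteren test adjusting for the randomization stratification factors (age group, sex, and site". These are the three randomization factors (protocol 7.2, SAP 3.3). Baseline severity is not among them.
- **Baseline NIAID.** The Schedule of Activities (protocol section 2) marks the scale at screening. SAP 4.8 summarises "other baseline efficacy measures including NIAID ordinal assessment" by arm, without testing.
- **Where it meets the primary endpoint.** SAP 4.14 analyses VFD separately for baseline score 3 and for 4 or 5 (Table 33 in SAP 5.1). SAP 4.12.2 adds only VFD among survivors. No analysis gives one overall treatment comparison of VFD adjusted for baseline score.
- **Range of severity.** Patients with ARDS or an immediate need for IMV are excluded (protocol 6.2), so baseline scores are effectively 3 to 5. Score 3 is non-invasive ventilation or high-flow oxygen, the category next to invasive ventilation.

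**The concern.** The VFD score is driven by whether a patient is ventilated or dies, and baseline oxygen support is a natural candidate to predict both. The sponsor treats it as relevant enough to define a subgroup. It is not balanced by design, so the arms can differ by chance in their share of score-3 patients. SAP 4.8 would show such a difference and SAP 4.14 would give two separate subgroup answers, but nothing planned would say what the overall result looks like once severity is allowed for. At stake are how the one realised trial is interpreted and, if the score is strongly prognostic, some power.

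**Working it through.** **1. The plan's own power figure.** SAP 3.2 claims that 100 patients per arm "will have 81% power to detect a difference between the placebo group and the LY3127804 group" (rank-sum test, one-sided alpha 0.05). The IMV and death inputs are a "rate of 25% and mortality rate of 12.5% in the placebo group", both halved on LY3127804, with a mean difference of 3.0 VFD. Suppose all deaths fall among IMV patients, which fits the protocol 3.1 figures (25% ARDS x 50% fatality = 12.5%). Then:

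- The ordered categories death / ventilated survivor / never ventilated are 12.5 / 12.5 / 75% on placebo and 6.25 / 6.25 / 87.5% on LY3127804. Ventilated survivors must average 9 VFD to give the 3.0-day difference.
- P(LY3127804 better) + half P(tie) = 0.2266 + 0.3359 = 0.5625.
- Null SD = sqrt[201/(12 x 100 x 100) x (1 - 0.538)] = 0.0278, where 0.538 is the sum of cubed pooled proportions (0.09375, 0.09375, 0.8125).
- Power = Phi(0.0625/0.0278 - 1.645) = 73%.

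Power is 81% if about 60% of deaths occur in IMV patients, 84% if death and IMV are independent, and 90% if they do not overlap. The overlap is not stated, so the inputs bracket 81% without fixing it, and I do not call it an error. The simulations below use full overlap, so their reference level is about 73%.

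**2. Assumptions not in the documents.** 5, 10 or 20 sites; baseline NIAID 3/4/5 split 20/60/20; 40% aged 65 or over; 40% in one sex; higher risk in the older group; half of IMV patients die. Placebo IMV risk for scores 3/4/5 is none 25/25/25%, weak 35/25/15%, moderate 50/22/9% or strong 70/17/4%, each averaging 25%. Randomization is in blocks of 4 within age x sex x site, with the SAP 4.5 pooling rule. There were 3,000 trials per power scenario (Monte Carlo SE about 0.8 points) and 8,000 per null scenario.

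**3. Power (%).** The ANCOVA columns are rank ANCOVA on age, sex and site, without and then with NIAID.

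| Sites | Strength | van Elteren as planned | van Elteren, NIAID as extra stratum | ANCOVA without | ANCOVA with | Change |
|---|---|---|---|---|---|---|
| 5 | none | 72.8 | 64.0 | 73.9 | 73.3 | -0.6 |
| 5 | weak | 72.9 | 64.4 | 74.4 | 74.5 | +0.1 |
| 5 | moderate | 73.2 | 65.0 | 74.3 | 77.1 | +2.8 |
| 5 | strong | 73.4 | 66.1 | 74.9 | 81.7 | +6.8 |
| 10 | none | 70.5 | 57.9 | 73.6 | 73.5 | -0.1 |
| 10 | weak | 69.0 | 56.6 | 72.9 | 72.9 | 0.0 |
| 10 | moderate | 71.0 | 57.7 | 74.2 | 76.6 | +2.4 |
| 10 | strong | 71.2 | 55.2 | 73.5 | 80.9 | +7.4 |
| 20 | none | 65.1 | 47.9 | 71.9 | 71.4 | -0.5 |
| 20 | weak | 65.5 | 49.2 | 72.8 | 73.3 | +0.5 |
| 20 | moderate | 66.5 | 48.1 | 72.3 | 74.6 | +2.3 |
| 20 | strong | 63.7 | 45.6 | 70.8 | 80.3 | +9.5 |

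Crossing NIAID into the strata loses about 7-9, 12-16 and 16-18 points at 5, 10 and 20 sites. The share of patients in strata holding both arms falls from 99/96/88% to 87/74/58%. Runs with a 25/50/25 split, and with site kept or dropped, agreed: for example 75% to 78% (moderate) and 74% to 81% (strong). Allowing for simulation error, I take 2-4 points for moderate, 5-10 for strong, and a loss of at most about 1.

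**4. False-positive rate under the null (10 sites, one-sided 5%).** Unconditionally the planned test gives 4.8% (moderate) and 5.1% (strong). Among the roughly 6% of trials with 8-12 points more score-3 patients on placebo:

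| Strength | Planned test | Rank ANCOVA with NIAID |
|---|---|---|
| moderate | 9.2% | 4.6% |
| strong | 20.6% | 8.3% |

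The 25/50/25 runs gave 11% and 14% against 5% and 3%. With the same imbalance the other way, the planned test rejects in 1% of trials or fewer.

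**5. How likely and how large.** The SD of the imbalance is sqrt(2 x 0.20 x 0.80/100) = 5.7 points (4.2 at 10% prevalence, 6.5 at 30%). An imbalance of 10 points or more in either direction occurred in about 8% of simulated trials. For a 1-SD imbalance at 25% prevalence, the SD is sqrt(2 x 0.25 x 0.75/100) = 6.1 points. If score-3 placebo risk is 50%, the other patients average (0.25 - 0.125)/0.75 = 16.7%. With no treatment effect the IMV difference shifts by 0.061 x 0.333 = 2.0 points. If treatment halves risk uniformly, it shifts by 0.0306 x 0.333 + 0.0306 x 0.167 = 1.5 points, 12% of the planned 12.5.

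**The case against.** The strongest reply is that nothing here is an error. Analysing by the factors used in randomization is a valid, pre-specified choice, and randomization holds the type I error at about 5%. A 1.5 to 2 point shift is small beside the standard error of the IMV difference, sqrt(0.25 x 0.75/100 + 0.125 x 0.875/100) = 5.4 points, which already includes this chance variation. The plan does not disregard severity either: SAP 4.8 would reveal an imbalance, and SAP 4.14 reports VFD by baseline score. All of that stands. It makes this a question of precision and of interpreting the realised trial, not of validity. It does not supply an adjusted overall comparison.

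A second objection is timing. SAP 4.16.1 describes the interim futility analysis in the past tense, on an unblinded snapshot that included VFD. The primary test is named in the protocol, and protocol 10.3.1 requires an amendment when a principal feature changes. Replacing the test now invites questions about motive for an uncertain gain. This stands too, and it is why the fix has a fallback.

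Two stronger readings are tempting. A reader might infer that adjustment is a free gain in power. The documents do not support that: they give neither the prevalence of each score nor IMV risk by score, the gain is nil under weak prognosis, and adding NIAID in the obvious way, as another stratum, loses power. A reader might also set the planned test at 20 assumed sites (64-67%) against the adjusted ANCOVA (up to 80%) and credit NIAID with the whole gap. Much of it comes from sparse site strata, since ANCOVA without NIAID already reaches 71-73% there, and the number of sites is not stated.

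**Conclusion.** The point holds as a worthwhile, low-cost improvement and not as a defect in validity. Given a score-3 excess on placebo of about 10 points, the planned test's one-sided false-positive rate is roughly 9-21% if baseline NIAID is moderately to strongly prognostic, against about 3-8% with covariate adjustment. The expected power change is about 0 points (none or weak), 2-4 (moderate) or 5-10 (strong). These figures rest on assumed score prevalence, risk by score, site numbers and full overlap of death with IMV. The conditional rates come from about 6% of the null trials and are correspondingly rough. If the score turns out weakly prognostic, adjustment changes little either way.

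**What to change.** Before final unblinding, and by staff blinded to the interim data, pre-specify in SAP 4.12 a rank ANCOVA (covariate-adjusted Wilcoxon) of the VFD score on treatment, age group, sex, pooled site and baseline NIAID (3/4/5). Keep site, because it is a randomization factor. Enter NIAID as a covariate, not as a further van Elteren stratum. State how a missing baseline score is handled.

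- **If the primary test can still be changed by amendment:** make this the primary analysis and report the van Elteren test as a sensitivity analysis.
- **If not:** keep van Elteren as primary and add this to SAP 4.12.2 as the key supportive analysis, to be read alongside it.

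Cost: SAP wording and a few lines of code, with no new data collection. Replacing the primary test also needs a protocol amendment and carries possible credibility questions because the unblinded interim has already taken place. The supportive route largely avoids both.

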4.12.2 Additional Analyses of the Primary Outcome

The number of ventilator free days among survivors will also be reported.

4.12.3 Secondary Efficacy Analyses

Secondary end points will be described and compared between treatment groups.

4.12.3.1 Alive and Respiratory Failure Free Complete Response

Complete Response is defined as being alive and never requiring mechanical ventilator support (at any point while on trial) through day 28.

The rates of complete response and non-response will be summarized by treatment group and by the stratification factors. See section 4.1 for details on the methods to be used to test the differences between LY3127804 and placebo.

Ninety percent confidence interval for the difference in proportions (LY3127804 – placebo) will be reported.

Patients for whom complete response status cannot be determined will be considered non-responders. See section 4.3.2 for details on NRI.

4.12.3.2 NIAID Ordinal Assessment

The NIAID will be assessed daily and defined as the lowest score achieved for that day.

The scoring is based on the clinical status of the patient as described below.

NIAID Score	Description
1	Death

2	Hospitalized, on invasive mechanical ventilation or extracorporeal membrane oxygenation (ECMO)
3	Hospitalized, on non-invasive ventilation or high flow oxygen devices
4	Hospitalized, requiring supplemental oxygen
5	Hospitalized, not requiring supplemental oxygen - requiring ongoing medical care (COVID-19 related or otherwise)
6	Hospitalized, not requiring supplemental oxygen - no longer requires ongoing medical care
7	Not hospitalized, limitation on activities and/or requiring home oxygen
8	Not hospitalized, no limitations on activities

The lowest value from Day 1 through Day 28 for a patient on the NIAID ordinal scale will be analyzed using the van Elteren test adjusting for the randomization stratification factors. The number need to treat (NNT) to prevent one patient from progressing to level 2 or 1 will be calculated. Mean values will be calculated and differences in treatment effect estimates at Days 7, 14 and 28 will be analyzed. Mean value by treatment group will be plotted over time.

[figure not shown]
Time to the first 2-point improvement on the NIAID scale will be analyzed between treatment groups. The time for subjects who did not achieve 2-point improvement will be censored at day 28 and stratification will be ignored in this analysis. A Kaplan-Meier plot with log-rank test will be used to compare treatment groups.

The stacked bar plot(s) representing the proportion of subjects in each score by treatment arm over time will be generated with stratification ignored. An example of such plot is as follows. The details of the score will be included in the footnote of the plot.

In addition to the stacked bar plot based on the original NIAID scores, another stacked bar plot that lumps NIAID scores into four categories will be generated. The four new categories are:

- a. Death (NIAID score = 1),
- b. IMV/ECMO (NIAID score = 2),
- c. Requiring O₂ or medical care (NIAID scores = 3, 4, 5), and
- d. Not requiring O₂ nor medical care (NIAID scores = 6, 7, 8).

Figure 2.0 Example of a Stacked Bar Plot:

4.12.3.3 28-day Mortality

Mortality will be defined as 28-day all-cause mortality, defined as 672 hours from the time of randomization. All patients will be classified as either “alive at Study Day 28” or, if dead, “dead at Study Day 28.” Patients whose mortality status cannot be determined will be classified as “dead at Study Day 28.” The difference between treatment groups will be analyzed.

The 60-day mortality will be analyzed in a similar fashion.

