Unless otherwise noted, treatment comparisons of quantitative variables will be made using a restricted maximum likelihood-based mixed-effects model of repeated measures (MMRM). The model will include treatment, age group, sex, and site as fixed categorical effects, and, if applicable, study day as a continuous effect and treatment-by-study day interaction. The covariance structure to model the within-patient errors will be unstructured. If the available data cannot support the covariance structure (e.g., due to missing values), other structures will be attempted. If the unstructured covariance matrix results in a lack of convergence, the heterogeneous Toeplitz (TOEPH) covariance structure, followed by the heterogeneous autoregressive [ARH(1)] covariance structure, followed by the compound symmetry structure will be used. The first structure to yield convergence will be used for inference. The NewtonRaphson with ridging optimization technique will be used to aid with convergence. The Kenward-Roger approximation (KR2) will be used to estimate the denominator degrees of freedom and adjust standard errors. Type III tests based on the LS means will be used for the statistical comparison; the 90% CI will also be reported.

All tests of treatment effects will be conducted at a 1-sided alpha level of 0.05, unless otherwise stated. No adjustments for multiple comparisons will be made.

All computations for statistical analyses will be performed using SAS® software, Version 9.4 or later. All SAS programs used in the production of statistical summary outputs will be validated with independent programming prior to finalization. In addition, all program outputs will be independently reviewed. The validation process will be used to confirm that all data manipulations and calculations were accurately done. Upon completion of validation and quality review procedures, all documentation will be collected and filed by the project statisticians.

When implementing parametric methods of analysis, the distribution of analysis variables will be examined to determine if model assumptions are satisfied. Transformations or nonparametric methods of analysis may be added as sensitivity analyses if warranted. Whenever alternative methods of analysis are required, the description of the new method along with the rationale for its use will be documented in the Clinical Study Report (CSR).

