4.14 Subgroup Analyses

The primary end point will be analyzed for the following subgroups:

- Patients who are confirmed SARS-CoV-2 positive and otherwise o age group < 65 and ≥ 65 o sex o BMI < 30 and ≥ 30 o Patients that receive one dose and two doses of study drug o Patients who reach NIAID ordinal scale score = 2 within day 4 and those who do not o Patients with baseline NIAID ordinal scale score of 3, and those with baseline score of 4 or 5
- Patients who received remdesivir and those who do not.

For endpoints which do not consider mortality, subgroup analyses of survivors only may be conducted if appropriate.

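### The worst-NIAID-score analysis does not adjust for baseline NIAID score; the test is valid but gives up power, by about 5 to 40 points under plausible assumptions

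*SAP*

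**What the plan says.** SAP 4.12.3.2 reduces each patient's daily scores to one number, "The lowest value from Day 1 through Day 28 for a patient on the NIAID ordinal scale", and tests it with a van Elteren test. SAP 3.3 and Protocol 7.2 give the stratification factors as age group, sex and site. Baseline NIAID score is not among them.

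The score is nevertheless available before treatment. The Schedule of Activities (Protocol Section 2) records it at screening and then daily. SAP 4.8 summarises "other baseline efficacy measures including NIAID ordinal assessment". SAP 4.14 plans a subgroup analysis of the primary endpoint in "Patients with baseline NIAID ordinal scale score of 3, and those with baseline score of 4 or 5".

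The documents state no power for the worst-score analysis. The design figures in SAP 3.2 concern ventilator-free days: "A sample size of 100 in each group will have 81% power to detect a difference", assuming "intermittent mandatory ventilation (IMV) rate of 25% and mortality rate of 12.5% in the placebo group" and "50% improvement in IMV rate and mortality rate for the LY3127804 group relative to placebo". SAP 4.1 sets the level: "All tests of treatment effects will be conducted at a 1-sided alpha level of 0.05, unless otherwise stated".

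**The concern.** A patient who neither dies nor is ventilated has a worst score that cannot be above the entry level and will often equal it. A stable patient who enters on high-flow oxygen (score 3) therefore ranks below a stable patient who enters without oxygen (score 5), whichever arm each is in. Under the design rates this group is 75% of placebo and 87.5% of LY3127804 patients. Ranking them against one another adds spread that the treatment did not cause.

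A mix of entry scores is likely. Protocol 6.2 excludes patients who have ARDS or need immediate ventilation, not those on high-flow oxygen. Protocol 6.1 can be met by symptoms plus infiltrates with no oxygen requirement.

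At stake is the sensitivity of a secondary endpoint. A null result could reflect the choice of strata rather than the absence of an effect.

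**Working it through.** **Inputs from the documents.** 100 per arm, 1:1; one-sided 0.05; ventilation 25% versus 12.5%; death 12.5% versus 6.25%. Deaths are taken as half of ventilated patients (25% x 50% = 12.5%, matching the 25% ARDS and 50% fatality figures in Protocol 3.1). Hence score 1: 12.5% versus 6.25%; score 2: 12.5% versus 6.25%; score 3 or better: 75% versus 87.5%.

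**Inputs assumed, because the documents do not give them.** The mix of baseline scores 3/4/5, the risk of progression by baseline score, one-level worsening among patients who do not progress to 1 or 2, and the number of sites.

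**The plan's own figure.** The 81% is for ventilator-free days. With deaths nested in ventilation, a tie-corrected Wilcoxon test gives 73.7%. Values of 80-82% appear if about 30-40% of deaths occur without ventilation, which the documents do not state. The 81% is therefore no benchmark for the NIAID test.

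**Closed-form check.** Take a 25/50/25 mix, equal risk, and non-progressors staying at their entry score.

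- Placebo, scores 1 to 5: 12.5, 12.5, 18.75, 37.5, 18.75%. LY3127804: 6.25, 6.25, 21.875, 43.75, 21.875%.
- P(LY3127804 better) + half P(tie) = 0.5625, an effect of 0.0625.
- Null SE = sqrt[(N+1)/(12n²) x (1 - Σp³)], with N = 200, n = 100 and p the pooled proportions.
- Ignoring baseline: Σp³ = 0.0855, SE = 0.0391, z = 0.0625/0.0391 = 1.60, power = Φ(1.60 - 1.645) = 48%.
- Within a baseline level only three outcomes remain (1, 2, unchanged), pooled 0.09375, 0.09375, 0.8125: Σp³ = 0.538, SE = 0.0278, z = 2.25, power = Φ(0.60) = 73%.

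The effect is the same in both lines. Only the SE differs, because stable patients in the same stratum are now tied.

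With 3:2:1 risk (37.5/25/12.5%) the effect shrinks too. Preventing progression leaves more patients at score 3 on LY3127804 (20.3% versus 15.6%), and these rank low. The effect falls to 0.0508, z = 0.0508/0.0391 = 1.30, power = Φ(-0.35) = 36%.

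**Simulated trials** (20,000 each, no other strata, non-progressors at entry score):

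| Baseline 3/4/5 | Risk by score | Baseline ignored | Stratified by baseline | Gain (points) |
|---|---|---|---|---|
| 10/70/20 | equal | 52.7% | 73.1% | 20 |
| 25/50/25 | equal | 48.6% | 73.5% | 25 |
| 25/50/25 | 3:2:1 | 36.3% | 74.1% | 38 |
| one third each | 3:2:1 | 34.1% | 74.5% | 40 |
| one third each | 6:2:1 | 25.7% | 76.9% | 51 |
| all at 4 | equal | 73.5% | 73.5% | 0 |

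**One-level worsening.** Suppose non-progressors also drop a level (20% from 4, 30% from 5). With no drug effect on that drop the gain is 6 to 31 points. If the drug halves it, power is 43-78% ignoring baseline and 86-91% stratified, a gain of 12 to 48.

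**Keeping age and sex as strata.** In four scenarios (mix 25/55/20 or 40/45/15; 20-35% of non-ventilated score 4-5 patients worsen one level on placebo, a quarter fewer on drug), age x sex gives 47/50/58/43% and age x sex x baseline gives 76/75/75/76%. The gains are 29/25/17/33 points. Over a wider set, with equal to 3:2:1 risk and with or without one-level worsening, the ranges are roughly 35-65% and 52-79%.

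**Site is a separate component.** At an assumed 20 sites, the planned age x sex x site strata give 39/41/47/35% in the same four scenarios, which is 8/9/11/8 points below age x sex. The cost is about 6 to 13 points at 12 to 20 sites, and 1 to 3 points at 8.

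**Starting at Day 2 without baseline adjustment.** 48.2% becomes 47.9%, 36.4% becomes 38.3%, and 52.0% becomes 48.3%: a change of -4 to +2 points.

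**The case against.** The strongest reply is that this is an efficiency choice for a secondary endpoint with no stated power, no place in a hierarchy and no multiplicity adjustment (SAP 4.6). The main contrast is also tested elsewhere. Complete Response (SAP 4.12.3.1) compares being alive and never ventilated, is untouched by spread over scores 3 to 5, and has about 73.5% power for 25% versus 12.5%. Dropping site departs from the randomization factors, and SAP 4.16.1 describes the interim analysis as already done, so a change needs justification. All of this stands. It limits the weight of the point and shapes the remedy, but does not make the omission a good choice.

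A reader might infer several stronger things that the documents and the arithmetic do not support:

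- *That counting Day 1 causes the loss.* Patients who stay at their entry level carry the same spread into Day 2, so starting later recovers almost nothing.
- *That the number needed to treat is affected.* It concerns progression to level 2 or 1. Patients needing immediate ventilation are excluded at entry (Protocol 6.2), so spread over scores 3 to 5 does not enter it.
- *That baseline severity swamps the effect or invalidates the test.* Randomization protects the type I error, and the analysis without baseline keeps about 26-78% power across the scenarios above.
- *That one firm figure can be given.* The size rests on assumptions, and a comparison that adds baseline and removes site together mixes two effects.

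**Conclusion.** The point holds as a loss of efficiency, not an error of validity. Adding baseline NIAID score to age and sex strata would gain about 5 to 40 points of power under the SAP's design effect with entry scores spread over 3 to 5. The limits are zero if all patients enter at one level, which is not what SAP 4.14 expects, and about 50 points with a 6:2:1 risk gradient. Removing sparse site strata is a second, smaller and less certain gain, because it depends on the number of sites and on pooling under SAP 4.5. The direction is secure wherever entry scores vary. The size is conditional on the baseline mix, the risk gradient and one-level worsening, none of which the documents state.

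**What to change.** In SAP 4.12.3.2, stratify the van Elteren test for this endpoint by baseline NIAID score (3, 4, 5) with age group and sex. Alternatively, use a proportional-odds model with baseline score, age group and sex as covariates. Define baseline as the score recorded before the first dose. Keep the version with site as a sensitivity analysis. The Day 1 to Day 28 window and the number-needed-to-treat calculation can stay as they are.

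Because the interim analysis has been conducted, blinded personnel should make and document the change, with its rationale, before database lock.

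The cost is SAP wording and a small programming change; no new data are needed. The downside is that site is not in the strata for this one secondary analysis, while the primary and length-of-stay tests keep it.
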